#### **Audit size for BIRC assessed PFS**

The audit size of the sample-based BIRC assessment will be 40% of all randomized patients. Based on the audit size calculation approach proposed by Dodd, et. al (2011), assuming investigator and BIRC assessments are similar and the estimated log of investigator-based HR is -0.40 (i.e., HR=0.67), the audit size of 40% will ensure that the upper bound of a one-sided 95% CI for BIRC-based log-hazard ratio has 86% probability of being below 0 (i.e. HR < 1) if the correlation between investigator assessment and BIRC assessment is 0.7 (the estimated

correlation based on data from the BELLE-2 [CBKM120F2302] study in metastatic breast cancer).

### **Power for analysis of overall survival**

OS will be compared between the two treatment arms, provided that the primary endpoint, PFS, is statistically significant. The power statements for overall survival below are therefore conditioned on significant primary PFS result. Estimate of first line median OS with fulvestrant alone is not published. However the median OS with fulvestrant alone in first line setting is expected to be between 34 months (letrozole alone, [Mouridsen 2003](#)) and 38 months (anastrozole alone, FACT trial, [Bergh et al 2012](#)) based on results from endocrine based monotherapy studies. For sample size calculation, we assume the median OS for fulvestrant alone in first line to be 38 month. Median OS for fulvestrant in relapsed post-menopausal advanced breast cancer patients is estimated to be between 19 months (SoFEA trial, [Johnston et al 2013](#)) and 26 months (CONFIRM trial, [Di Leo et al 2014](#)). For sample size calculation, the mOS for fulvestrant in second line is assumed to be 26 months. Based on the expected split of first line and second line patients mentioned above, the median overall survival of control arm is estimated via simulation to be approximately 30 months. It is hypothesized that adding ribociclib to fulvestrant will result in a 29% reduction in the hazard rate for OS (corresponding to an increase in median survival to 42 months). To detect a hazard ratio of 0.71 with 85% cumulative power, a maximum of 353 deaths need to be observed, (using a log-rank test and a 3-look [superiority only] group sequential design at one-sided cumulative 2.5% level of significance). The sample size calculation was conducted with software package East 6.3.

Based on the number of patients planned to be randomized and 10% dropout rate by the time of OS final analysis, it is estimated that these 353 deaths will be observed at approximately 56 months after the randomization of the first patient. Therefore the estimated time for the final OS evaluation will be 30 months after the primary analysis of the PFS endpoint.

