The distribution function of OS will be estimated using the Kaplan-Meier method. The median OS along with 95% confidence intervals will be presented by treatment group. The stratified Cox regression will be used to estimate the hazard ratio (HR) of OS, along with 95% confidence interval.

Since the secondary endpoint of OS was met at the second interim analysis, no further formal analyses of OS are planned. If any descriptive analyses of OS are performed after allowing patients ongoing on study treatment in the placebo arm to cross-over to the LEE011 combination arm (permitted after the study met its primary and key secondary endpoints), appropriate sensitivity analyses will be considered and described in the SAP, for example censoring OS at the date of first LEE011 treatment for patients in the crossover analysis set.

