**Table 10-1 Estimated timelines for interim and final analyses**

Months after randomization of the first patient	PFS events	Power (%) against a hazard ratio of 0.67	OS events	Cumulative Conditional Power (%) against hazard ratio of 0.71
26	364 (100%)	90	161(46%)	14
39	--	--	263(75%)	60
56	--	--	351(100%)	85

Statistical significance of OS will only be declared if significance for primary PFS analysis has been declared.

At the time of final PFS analyses, both PFS and interim OS analysis will be performed by the Sponsor's clinical team. Investigators and patients will remain blinded to study treatment and all patients will continue to be followed for OS until the final OS analysis (or earlier if OS reaches statistical significance at any of the interim analyses).

Since the study has met its primary endpoint (PFS) and the secondary endpoint (OS), any analysis and update after protocol amendment 4 will be descriptive.

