3.8.2.1 Overall survival

Comparing the overall survival (OS) between ribociclib +fulvestrant and placebo+fulvestrant is a secondary objective in this study. OS is defined as the time from date of randomization to date of death due to any cause. If a patient is not known to have died at the time of analysis

cut-off, then OS will be censored at the date of last contact. Assuming proportional hazards for OS, the following statistical hypotheses will be tested:

$$H_{02}: \theta_2 \geq 0 \text{ vs. } H_{A2}: \theta_2 < 0$$

Where θ_2 is the log OS hazard ratio (fulvestrant+ ribociclib arm vs. fulvestrant + placebo arm). The analysis to test this hypothesis is a stratified log-rank test at an overall one-sided 2.5% level of significance. The stratification will be based on the randomization stratification factors.

A maximum of 3 analyses are planned for OS: at the time of the analysis for PFS (provided PFS is significant), at which point a total 161 deaths (46% of OS events) are expected, after 263 events (75% of OS events) have been documented, and a final analysis for OS when 351 deaths (100% of OS events) are expected (expected 56 months from date of first patient to be randomized).

OS tests will be carried out using a Lan-Demets (O'Brien-Fleming) alpha spending function. OS will only be tested if the primary efficacy analysis has been shown to be statistically significant. Analyses will be based on the FAS population according to the randomized treatment group and strata assigned at randomization. All deaths recorded up to the cut-off date will be included in the analysis. The survival distribution of OS will be estimated using the Kaplan-Meier method, and Kaplan-Meier curves, medians and 95% confidence intervals of the medians intervals along with the proportion of patients alive at 6 month interval starting from 12 month will be presented for each treatment group. The hazard ratio for OS will be calculated, along with its 95% confidence interval, using a stratified Cox model using the same stratification factors as the log-rank test.

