3.14.2 Overall Survival

Overall survival will be compared between the two treatment groups, provided the primary endpoint PFS is statistically significant favoring the test treatment arm (fulvestrant + ribociclib). A hierarchical testing procedure will be adopted in this study and the treatment effect on OS will be tested only if the primary efficacy endpoint PFS is statistically significant. A maximum of 3 analyses are planned for OS: at the time of analysis for PFS (provided PFS is significant), at which point a total of 161 deaths are expected, after 263 events have been documented, and a final analysis for OS when 361 deaths are expected (expected 56 months from date of first patient to be randomized).

An α -spending function according to Lan-DeMets (O'Brien-Fleming), (as implemented in East 6.3) along with the testing strategy outlined below will be used to maintain the overall type I error probability (Lan and DeMets 1983). This guarantees the protection of the 2.5% overall level of significance across the two hypotheses and the repeated testing of the OS hypotheses in the interim and the final analysis (Glimm 2010). The trial allows for the stopping of the study for a superior OS result, provided the primary endpoint PFS has already been shown to be statistically significant favoring the test treatment arm (fulvestrant + ribociclib). Further, the exact nominal p-values that will need to be observed to declare statistical significance at the time of these analyses for OS will depend on the number of OS events that have been observed at the time of these analyses and the α for OS already spent at the time of earlier analyses.

The operating characteristics for OS are shown in Table 3-9 considering the hierarchical testing strategy of PFS and OS. The probabilities shown in Table 3-9 are conditional on PFS being statistically significant.

Statistical properties of the group sequential design are summarized in Table 3-9.

[figure not shown]
Table 3-9 Projected timelines for interim and final analyses

[figure not shown]
Months after randomization of the first patient	PFS events	Cumulative Power (%) against a hazard ratio of 0.67	OS events	Cumulative Conditional Power (%) against hazard ratio of 0.71
26	364 (100%)	95	161(46%)	14
39	--	--	263(75%)	60
56	--	--	351(100%)	85

Statistical significance of OS will only be declared if significance for primary PFS analysis has been declared.

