3.17 Power for analysis of secondary variable

OS will be compared between the two treatment arms, provided that the primary endpoint, PFS, is statistically significant. The power statements for overall survival below are therefore conditioned on significant primary PFS result. Estimate of first line median OS with fulvestrant alone is not published. However the median OS with fulvestrant alone in first line setting is expected to be between 34 months (letrozole alone, [Mouridsen 2003](#)) and 38 months (anastrozole alone, FACT trial, [Bergh et al 2012](#)) based on results from endocrine based monotherapy studies. For sample size calculation, we assume the median OS for fulvestrant

alone in first line to be 38 month. Median OS for fulvestrant in relapsed post-menopausal advanced breast cancer patients is estimated to be between 19 months (SoFEA trial, [Johnston et al 2013](#)) and 26 months (CONFIRM trial, [Di Leo et al 2014](#)). For sample size calculation, the median OS for fulvestrant in second line is assumed to be 26 months. Based on the expected split of first line and second line patients mentioned above, the median overall survival of control arm is estimated via simulation to be approximately 30 months. It is hypothesized that adding ribociclib to fulvestrant will result in a 29% reduction in the hazard rate for OS (corresponding to an increase in median survival to 42 months). To detect a hazard ratio of 0.71 with 85% cumulative power, a maximum of 351 deaths need to be observed, (using a log-rank test and a 3-look [superiority only] group sequential design at one-sided cumulative 2.5% level of significance). The sample size calculation was conducted with software package East 6.3.

Based on the number of patients planned to be randomized and 10% dropout rate by the time of OS final analysis, it is estimated that these 351 deaths will be observed at approximately 56 months after the randomization of the first patient. Therefore the estimated time for the final OS evaluation will be 30 months after the primary analysis of the PFS endpoint.

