4.3 Group sequential design used in Phase III studies

The statistical methodology for the interim analyses of OS will be based on group sequential methodology with efficacy stopping boundaries defined by type I error spending functions.

This approach is flexible in dealing with any deviations from the targeted event totals, or unexpected changes to the plan.

If the exact number of events observed at the interim and final analyses deviates from the target numbers described in the protocol, the actual critical boundaries will be derived using the pre-specified error spending functions and the actual numbers of events observed.

- At interim analyses, information fractions will be computed as the ratio of the number of events observed at the considered interim analysis relative to the number targeted for the final analysis, as described in the sample size section of the protocol.
- At the final analysis, the critical value will be calculated using the exact number of observed events at the final cut-off date, considering the α -levels spent at interim analyses and considering the actual correlation among the test statistics, in order to achieve a cumulative type I error smaller than the desired significance level (i.e. smaller than 2.5% for a one-sided test and smaller than 5% for a two-sided test).

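### The final OS target is given as 351, 353 and 361 deaths, and SAP 4.3 ties the OS boundary to the 353 section; separately, Protocol Table 10-1 gives 90% PFS power where 364 events give 95%

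*Protocol*

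**What the plan says.** **Final OS target.** Three numbers are given for one analysis.

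- 351 deaths: the protocol summary, protocol 10.5.1, 10.7.2 and Table 10-1, and in the SAP for the primary PFS analysis 3.8.2.1 ("a final analysis for OS when 351 deaths (100% of OS events) are expected"), Table 3-9 and 3.17 ("To detect a hazard ratio of 0.71 with 85% cumulative power, a maximum of 351 deaths need to be observed").
- 353 deaths: protocol 10.8, twice ("To detect a hazard ratio of 0.71 with 85% cumulative power, a maximum of 353 deaths need to be observed" and "it is estimated that these 353 deaths will be observed at approximately 56 months after the randomization of the first patient").
- 361 deaths: the text of SAP 3.14.2 ("a final analysis for OS when 361 deaths are expected"). Table 3-9 in the same section shows 351 (100%).

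**Boundary rule.** SAP 4.3 computes each interim information fraction as the observed deaths "relative to the number targeted for the final analysis, as described in the sample size section of the protocol".

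**Status of OS testing.** Protocol 10.5.1 records: "Since the secondary endpoint of OS was met at the second interim analysis, no further formal analyses of OS are planned".

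**PFS power.** In Table 10-1 the column "Power (%) against a hazard ratio of 0.67" reads 90 at 364 events. Protocol 10.8, SAP 3.16 and SAP Table 3-9 give 95% for the same events and hazard ratio. Protocol 10.8 also explains that power rose from 90% to 95% mainly because the futility look was dropped.

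**Two further leftovers.** Protocol 10.5.1 calls the OS design four-look, although three analyses are listed there, in 10.7.2 and in 10.8. Protocol 10.4.2 describes an interim look for PFS, which 4.2 and 10.7.1 say is not planned.

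**The concern.** Protocol 10.8 and SAP 3.17 contain almost the same sentence (same hazard ratio, power, number of looks and alpha) and differ only in the number of deaths. On its own that would be a typing slip. SAP 4.3 gives it an effect: the spending function needs a denominator, and the SAP sends the reader to the protocol section that says 353 while its own tables define 351 as full information. The plan therefore allows two different thresholds at each interim look.

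The second look is the one at which OS was declared, and no formal OS test follows it. The threshold behind a survival claim should be derivable from the plan without ambiguity, and here it is not.

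The 90% in Table 10-1 is a stated operating characteristic that does not belong to the current design. A reader relying on that table would think the primary analysis had twice the type II error it was planned with (10% instead of 5%).

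**Working it through.** **Inputs**

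- One-sided alpha 0.025, three looks, efficacy stopping only, OS hazard ratio 0.71 (protocol 10.8, SAP 3.17).
- Planned deaths 161 and 263 at the first two looks (protocol Table 10-1, SAP Table 3-9).
- Spending function α(t) = 2 − 2Φ(z₀.₀₁₂₅/√t) (SAP 4.3.1).
- 2:1 randomization, so information per event is (1/3)(2/3) = 2/9.
- PFS: 364 events, hazard ratio 0.67, no interim look.

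**OS.** With D the final target, the fractions are t₁ = 161/D, t₂ = 263/D and t₃ = 1. Boundaries come from multivariate normal integration so that cumulative type I error equals α(t) at each look. Power uses drift √(D × 2/9) × |ln 0.71|.

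| | D = 351 | D = 353 | D = 361 | Printed (tables) |
|---|---|---|---|---|
| Fraction, look 1 | 45.87% | 45.61% | 44.60% | 46% |
| Fraction, look 2 | 74.93% | 74.50% | 72.85% | 75% |
| One-sided p, look 1 | 0.000935 | 0.000904 | 0.000790 | – |
| One-sided p, look 2 | 0.009309 | 0.009115 | 0.008380 | – |
| Cumulative power, look 1 | 14.42% | 14.20% | 13.33% | 14 |
| Cumulative power, look 2 | 60.67% | 60.36% | 59.15% | 60 |
| Cumulative power, final | 85.02% | 85.23% | 86.04% | 85 |

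The plan's stated 85% is reproduced by both 351 and 353. Both also round to 46% and 75%. Only 361 fails, since it gives 45% and 73%. The printed 60 at look 2 is nearer to 353 (60.36) than to 351 (60.67, which rounds to 61), but that is too fine to decide the matter. The printed figures therefore cannot show which denominator was meant.

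Hazard ratio boundary at 263 deaths: exp(−b₂/√(263 × 2/9)), with √(263 × 2/9) = 7.645.

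- D = 351: b₂ = 2.3531, giving 0.7351.
- D = 353: b₂ = 2.3609, giving 0.7343.

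The ratio of look-2 thresholds is 0.009309/0.009115 = 1.021. The documents do not give the observed deaths, so I varied them by assumption: 120, 161 or 180 at look 1 and 250, 263 or 275 at look 2. The ratio stays between 1.020 and 1.023.

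**PFS.**

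- Power at 364 events: Φ(√(364 × 2/9) × |ln 0.67| − 1.96) = Φ(8.994 × 0.4005 − 1.96) = Φ(1.642) = 0.950.
- Events needed for 90%: (1.960 + 1.282)²/(2/9 × 0.4005²) = 294.8, so 295.

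The 95% reproduces. The 90% does not.

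**The case against.** The conflicts themselves are not in dispute. The case on the other side concerns their weight and the remedy.

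- *The effect is negligible.* The hazard ratio boundary moves in the third decimal place, type I error is controlled either way, later analyses are descriptive, and nothing in the documents suggests the OS p-value was close to either threshold. All of this stands and limits how much the point can be said to matter.
- *The denominator may already be on record.* The final SAP says PFS and OS were summarized in previous study reports, which are not among these documents. If the boundary and its denominator are stated there, a cross-reference is enough.
- *The explicit fractions should govern.* The SAP prints 351 as 100% in two places and repeats the 10.8 paragraph with 351 in 3.17, so a general cross-reference may carry less weight. That is a fair reading, but it leaves 4.3 pointing to a section with another number.
- *Version.* The SAP containing 4.3 was written against protocol amendment 2, and the protocol supplied is amendment 4. The 10.8 wording at that time cannot be seen. The change lists for amendments 3 and 4 do not mention 10.8, so it probably did not change.
- *Form of the fix.* That SAP has already been used, so rewriting it is less suitable than a dated erratum or note to file. I accept this.
- *The leftovers mislead nobody in practice.* This is true. They are included only because they can be corrected at the same time.

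**Conclusion.** The concern holds. One analysis has three stated targets. The 361 is incompatible with its own table. The 351 and 353 are both arithmetically sound designs, so neither can be called the error on the printed figures alone. SAP 4.3 read literally gives the slightly stricter threshold. The difference at the second look is 0.0093 against 0.0091 one-sided at the planned death counts, and 2.0–2.3% in relative terms over the range of counts assumed above. Overall type I error is 2.5% with either denominator, provided it was fixed in advance. This is therefore a gap in traceability for a declared OS result, and it gives no ground to doubt the result.

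The 90% PFS power in Table 10-1 is wrong for the stated design. The correct figure is 95%, and no event trigger or test depends on it.

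The calculations assume proportional hazards, information of 2/9 per event and the SAP 4.3.1 spending function.

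**What to change.** By dated erratum or note to file:

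1. In protocol Table 10-1, change PFS power from 90 to 95.
2. In the text of SAP 3.14.2, correct 361 to the 351 in Table 3-9.
3. Reconcile 351 and 353 between protocol 10.8, the tables and SAP 4.3 by stating which denominator produced the OS boundary applied at each look, or by citing the study report that records it. The denominator should be reported as it was used and not chosen now.
4. If the denominator was not 353, confirm from the observed deaths that the OS conclusion also holds at the stricter 353 threshold.
5. In protocol 10.5.1, change four-look to three-look, and remove the PFS interim wording from 10.4.2.

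The cost is a few text corrections, one sentence on the denominator and one boundary recalculation from existing counts. No new data are needed.

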### **Sample size justification for PK collection**

Sparse PK sampling will be performed on approximately 150 patients ([Table 7-6](#)). Assuming a 2:1 ratio between the ribociclib and placebo arm, sparse plasma concentrations for ribociclib will be available in approximately 100 patients. Trough PK sampling will be performed in all remaining patients ([Table 7-7](#)). PK data collected from this study may also be combined with data from other studies to support a population PK analysis of ribociclib using non-linear mixed effect modeling. The choice of sampling time points was selected to ensure capture of Cmax. The aim of this analysis is to analyze the pharmacokinetics of ribociclib in a sample size as large as possible. This sample is anticipated to represent the covariate distributions in the targeted population. No specific hypothesis will be tested and therefore no specific sample size calculation has been performed. The decisions on number of sparse PK samples and number of patients needed are driven by feasibility.

## **11 Ethical considerations and administrative procedures**

### **11.1 Regulatory and ethical compliance**

This clinical study was designed, shall be implemented and reported in accordance with the ICH Harmonized Tripartite Guidelines for Good Clinical Practice, with applicable local regulations (including European Directive 2001/20/EC and US Code of Federal Regulations Title 21), and with the ethical principles laid down in the Declaration of Helsinki.

### **11.2 Responsibilities of the investigator and IRB/IEC/REB**

The protocol and the proposed informed consent form must be reviewed and approved by a properly constituted Institutional Review Board/Independent Ethics Committee/Research Ethics Board (IRB/IEC/REB) before study start. Prior to study start, the investigator is required to sign a protocol signature page confirming his/her agreement to conduct the study in accordance with these documents and all of the instructions and procedures found in this protocol and to give access to all relevant data and records to Novartis monitors, auditors, Novartis Clinical Quality Assurance representatives, designated agents of Novartis, IRBs/IECs/REBs and regulatory authorities as required.

### **11.3 Informed consent procedures**

Eligible patients may only be included in the study after providing written (witnessed, where required by law or regulation), IRB/IEC/REB-approved informed consent or, if incapable of doing so, after such consent has been provided by a legally acceptable representative of the patient. In cases where the patient's representative gives consent, the patient should be informed about the study to the extent possible given her understanding. If the patient is capable of doing so, he/she should indicate assent by personally signing and dating the written informed consent document or a separate assent form. Informed consent must be obtained before conducting any study-specific procedures (i.e. all of the procedures described in the protocol). The process of obtaining informed consent should be documented in the patient source documents. The date when a subject's Informed Consent was actually obtained will be captured in their CRFs.

Novartis will provide to investigators, in a separate document, a proposed informed consent form (ICF) that is considered appropriate for this study and complies with the ICH GCP guideline and regulatory requirements. Any changes to this ICF suggested by the investigator must be agreed to by Novartis before submission to the IRB/IEC/REB, and a copy of the approved version must be provided to the Novartis monitor after IRB/IEC/REB approval.

If there is any question that the patient will not reliably comply, they should not be entered in the study.

